#### **6.9.2.2 OLE**

AEs will be considered treatment emergent for the purpose of reporting in the OLE if they meet any of the following criteria:

- AE onset date is after the end of treatment in the DPC period (i.e., date of onset greater than the end of treatment date in the DPC period)
- AE is ongoing, and the severity worsens during the OLE (i.e., date of severity worsening is greater than the end of treatment date in the DPC period)

All summaries will be presented by final dose group (i.e., 40, 60 or 80) and overall for the OLE set.

If the day of onset of an AE is missing, then if the month and year of an onset date are on or after the date of randomization, the following rules will be applied:

- If month/year of the onset date is on or after the month/year of the end of treatment date in the DPC period, the AE will be considered treatment emergent;
- If month/year of the onset date is equal to the month/year of the end of treatment date in the DPC period, and the end date is present, the end date will be used to determine when the AE started. If the end date is on or after the end of treatment date in the DPC period, the AE will be considered treatment emergent; otherwise, if the AE stopped before randomization, then it will not be considered treatment emergent;
- If month/year of the onset date is equal to the month/year of the end of treatment date in the DPC period, and the end date is a partial date, the AE will be considered treatment emergent;
- If, despite implementing the above conventions, the onset date of the AE cannot be placed before, on, or after the end of treatment date in the DPC period, then the event will be considered treatment emergent.

Summaries of TEAEs will be presented using the MedDRA level hierarchy (system organ class, high level group term, high level term, and preferred term) as follows:

Overall (i.e., regardless of intensity or relationship to treatment)

By intensity grade (mild, moderate, severe)

By relationship to study medication (potential relationship to study treatment or unlikely/no relationship to study treatment) according to the mapping scheme below:

Related: will include all AEs with a relationship rating of “related” or “possibly related”

Not related: will include all AEs with a relationship rating of “Not related”

Unless otherwise specified, at each level of patient summarization in reporting the incidence of the AEs, a subject will be counted once if the subject reported one or more events. If more than one occurrence of an event is reported, the event of the worst intensity or the worst-case relationship assessment will be summarized.

TEAEs leading to premature discontinuation of study drug and serious TEAEs (SAEs) will also be summarized by treatment group and relationship. TEAEs leading to premature discontinuation of study drug will be defined as any TEAEs with an action taken regarding study medication equal to “permanently discontinued.”

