## 3 Study Design

This will be a phase 3, randomized, double-blind, placebo-controlled, multicenter study to evaluate the safety and efficacy of octreotide capsules in acromegaly patients who previously tolerated and demonstrated biochemical control on injectable SRL treatment.

Patients meeting the pre-defined withdrawal criteria, IGF-1  $\geq 1.3 \times \text{ULN}$  AND exacerbation of acromegaly clinical signs or symptoms compared to baseline, for 2 consecutive assessments, while treated for at least two weeks with 4 capsules per day, during the DPC period, will be rescued with injectable SRL treatment used prior to Screening and will continue to be followed per protocol until week 36. At week 36, these patients will be offered to enter the OLE period and receive octreotide capsules. Patients who do not complete the full 36-week DPC period will not be eligible to enter the OLE period and will not require further follow up beyond week 36.

Patients who discontinue study medication early during the DPC period for reasons other than the pre-defined withdrawal criteria, should continue to be followed per protocol until week 36. The Sponsor recommends re-initiation of their prior injectable SRL treatment (as rescue or escape medication) upon meeting the pre-defined withdrawal criteria described above. These patients will not be eligible to enter the OLE period and will not require further follow up beyond week 36.

Patients who discontinue study medication during the OLE period, for any reason, or have completed the 36-week DPC period on study medication and are ineligible or not opting to continue into the OLE period, will revert to their prior injectable SRL treatment (prior to Screening) or other treatment as determined by their physician. These patients will be followed-up for 12 weeks after end of treatment (EOT).

Database lock for the DPC period will occur after the last patient completes the DPC period. At this timepoint, the study will be unblinded and all data from the DPC period analysed. Interim analyses of the OLE period will be conducted periodically, after completion of the DPC period. Data collected post DPC period (week 36) in patients not entering the OLE period and those who entered the OLE period will be included in the OLE database.

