## 6.9 Safety Analyses

All safety analyses for data collected during the DPC period will be presented using the safety set. All safety analyses for data collected during the OLE will be presented using the OLE set (summaries by treatment group will be based on the treatment group in the DPC period). Safety analyses for the DPC period will only use data collected during the DPC period, and will exclude any safety data that was collected after a subject had discontinued study drug. Safety analyses for the OLE will include data collected during the OLE. No formal hypothesis testing will be conducted. Data will be summarized using appropriate descriptive statistics. Missing data will be maintained as missing, unless indicated.

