### **6.9.1.2 OLE Phase**

Octreotide capsules can be up-titrated or down titrated during the OLE. All patients will start on 60 mg/day and can either down titrate to 40 mg/day or up titrate to 80 mg/day, based on clinical and biochemical response.

In the OLE, the duration of study drug exposure (in days) will be summarized by the treatment group and overall, using descriptive statistics. Duration of study drug exposure will be calculated as date of last dose in the OLE– date of first dose in the OLE + 1.

The number and proportion of patients at each dose level (40, 60 and 80 mg/day) at the end of the OLE, will also be presented by treatment group and overall.

Compliance to each dose level of octreotide capsules from first dose in the OLE through the last visit of the OLE will be calculated and summarized by treatment group and overall, and also by the final target dose level achieved within each treatment group during the OLE.

For the purpose of analysis, compliance to each dose level during the OLE will be calculated as  $100 \times (\text{total number of capsules actually taken} / \text{total number of capsules expected to be taken})$ . This calculation will be used for each dose level the patient received during the OLE. The numbers and percentages of patients <75% compliant, 75-100% compliant, and >100% compliant will be tabulated.

The number of actual capsules taken for each dose level will be the total number of capsules dispensed – total number of capsules returned during the time the patient was on that particular dose.

The number of expected capsules taken for the target dose level will be derived as follows:

Dose Level	Expected Number of Capsules Taken
40 mg	2 capsules × (first day of the phase – last day of the phase)
60 mg	3 capsules × (first day of the phase – last day of the phase)
80 mg	4 capsules × (first day of the phase – last day of the phase)
Overall	Sum of expected number of capsules taken over all of the dose levels assigned

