### 6.9.2.1 DPC period

All AEs that occur after randomization (i.e., date of onset is on or after the date of randomization) and on or before the end of treatment (last dose of blinded study drug) in the DPC period will be considered Treatment Emergent Adverse Events (TEAEs) for the purpose of reporting in the DPC period, and will be summarized using frequency counts and percentages. Summaries will be presented by final dose group and treatment group (i.e., octreotide 40, 60, 80, overall and placebo) and overall for the safety set.

If the day of onset of an AE is missing, then if the month and year of an onset date are on or after the date of randomization, the following rules will be applied:

- If month/year of the onset date is on or after the month/year of randomization, the AE will be considered treatment emergent;
- If month/year of the onset date is equal to the month/year of randomization, and the end date is present, the end date will be used to determine when the AE started. If the end date is on or after randomization, the AE will be considered treatment emergent; otherwise, if the AE stopped before randomization, then it will not be considered treatment emergent;
- If month/year of the onset date is equal to the month/year of randomization, and the end date is a partial date, the AE will be considered treatment emergent;
- If, despite implementing the above conventions, the onset date of the AE cannot be placed before, on, or after randomization, then the event will be considered treatment emergent.

Summaries of TEAEs will be presented using the MedDRA level hierarchy (system organ class, high level group term, high level term, and preferred term) as follows:

- Overall (i.e., regardless of intensity or relationship to treatment)
- By intensity grade (mild, moderate, severe)
- By relationship to study medication (potential relationship to study treatment or unlikely/no relationship to study treatment) according to the mapping scheme below:
  - Related: will include all AEs with a relationship rating of “related” or “possibly related”
  - Not related: will include all AEs with a relationship rating of “Not related”
- Unless otherwise specified, at each level of patient summarization in reporting the incidence of the AEs, a subject will be counted once if the subject reported one or more events. If more than one occurrence of an event is reported, the event of the worst intensity or the worst-case relationship assessment will be summarized.

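### The open-label AE window opens at the last blinded dose, so a rescued patient's AEs on injected SRL can be tabulated as open-label capsule TEAEs

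*SAP*

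**What the plan says.** SAP 6.9.2.1 counts an AE in the DPC period if it starts on or after randomization and "on or before the end of treatment (last dose of blinded study drug) in the DPC period". DPC end of treatment is therefore a dosing date, not Week 36.

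SAP 6.9.2.2 counts an AE in the OLE when "AE onset date is after the end of treatment in the DPC period", or when "AE is ongoing, and the severity worsens during the OLE (i.e., date of severity worsening is greater than the end of treatment date" (again the last blinded dose). Results are shown by final dose (40, 60 or 80) and overall for the OLE set. Protocol 8.4.8.1 has the same two criteria.

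Other sections bear on the same events:

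- SAP 3 sends to the OLE database "Data collected post DPC period (week 36) in patients not entering the OLE period and those who entered the OLE period".
- SAP 6.9 says "Safety analyses for the OLE will include data collected during the OLE". It also says that DPC safety analyses "will exclude any safety data that was collected after a subject had discontinued study drug".
- SAP 6.9.1.2 computes OLE exposure as the last OLE dose date minus "date of first dose in the OLE + 1".
- Protocol 7.1 runs TEAEs from the first dose at Baseline to the end of the DPC period. SAP 1 lets the SAP prevail over the protocol.

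For a missing onset day, the DPC rule begins "If month/year of the onset date is on or after the month/year of randomization, the AE will be considered treatment emergent". The OLE rule copies this structure with the DPC end-of-treatment month in place of the randomization month. Its only exclusion, however, still tests whether the AE ended before randomization.

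**The concern.** Rescued patients have a stretch of follow-up, from the last blinded dose to Week 36, in which they take no study capsules and receive injected SRL. The OLE rule takes in that stretch. A patient rescued from placebo could contribute to an octreotide capsule column an event that began before any octreotide capsule was taken.

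The OLE is there to describe long-term safety and efficacy on capsules, so its AE tables should hold events that arose on capsules. Because other SAP sections point to a different cut, two programmers could build different OLE tables from the same data, each with a section to cite.

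**Working it through.** The plan states no figure on this point, so the check is one of date logic.

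**Who is affected.** Protocol 6.10.4 bars parenteral SRL during study medication, so rescue means that blinded capsules have stopped. SAP 3 and Protocol 5.3 offer rescued patients the OLE at Week 36. SAP 6.5 lists having met the withdrawal criteria as an OLE-only baseline characteristic, so the SAP expects these patients in the OLE set.

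**One illustrative patient.** Last blinded dose Week 14, AE onset Week 20 on injections, first open-label dose Week 36.

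- DPC TEAE (onset no later than last blinded dose): 20 > 14, so no.
- OLE TEAE as written (onset after last blinded dose): 20 > 14, so yes.
- On or after the first open-label dose: 20 < 36, so no. The onset is (36 − 20) × 7 = 112 days too early.

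If SAP 3 and 6.9 are applied first as a data filter, the second answer becomes no and the AE is in neither period's TEAE table. Under Protocol 7.1 it would be a DPC TEAE.

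**Length of the interval.** Interval = 36 − week of last blinded dose. The paths are assumptions, and the last dose is placed at the second qualifying assessment. Waiting for the IGF-1 result would shorten the interval.

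| Assumed path to rescue | Last blinded dose (week) | Interval (weeks) |
|---|---|---|
| Criteria met at Week 36 | 36 | 0 |
| Last escalation Week 24, first qualifying visit Week 28 | 30 or 32 | 6 or 4 |
| Escalations at Weeks 4 and 8, first qualifying visit Week 12 | 14 or 16 | 22 or 20 |
| Escalations at the Week 1 and 2 calls, first qualifying visit Week 4 | 5 or 6 | 31 or 30 |

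With an assumed 52-week OLE, the AE window divided by counted exposure is (52 + 4)/52 = 1.08 for a 4-week interval, (52 + 22)/52 = 1.42 for 22 weeks and (52 + 31)/52 = 1.60 for 31 weeks. The SAP plans counts and percentages, not rates, so this shows the mismatch with 6.9.1.2 and not an error in a planned statistic.

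**Partial dates.** Let D be the days from randomization to the last blinded dose. The first day of that calendar month is at most 30 days before the last dose, so an onset in that month is at least D − 30 days after randomization.

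- D = 35 (Week 5): 35 − 30 = 5 days after.
- D = 42 (Week 6): 42 − 30 = 12 days after.
- D = 252 (36 × 7, completer): 252 − 30 = 222 days after.

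Whenever D exceeds 30, such an AE cannot have ended before randomization. Take one known to have ended while the patient was still on blinded drug. The first OLE branch (month on or after the end-of-treatment month) makes it an OLE TEAE. The second branch (same month, end date known) neither includes nor excludes it. The DPC rule also counts it, so it can appear in both tables. This part reaches completers too.

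**The case against.** The strongest reply is that 6.9.2.2 should not be read alone. Its rule serves OLE reporting, SAP 6.9 describes OLE safety as data from the OLE, and SAP 3 cuts the database at Week 36. On that reading no injection-period AE reaches a capsule column. This is a fair reading, but it is not settled by the text: 6.9 says OLE analyses include OLE data, whereas for the DPC it restricts them to DPC data. The worsening criterion also names the OLE and then defines it by the DPC end-of-treatment date. Taking end of treatment to mean the EOT visit does not help, since Protocol 5.4 schedules that visit for patients who stop early.

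Other objections succeed in limiting the point:

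- A reader might infer that SAP 6.9.1.2 contradicts the AE rule. It is an exposure formula, so the two are mismatched, not contradictory.
- A reader might infer that AEs after stopping have no home in either document. Protocol 7.1 covers them to the end of the DPC period, and Protocol 3 calls the time to Week 36 follow-up for early discontinuers. The gap is between protocol and SAP. The missing listing is weak evidence, because SAP 6.9.2 names no AE listing at all, while 6.9.3 to 6.9.6 send post-discontinuation data to listings.
- A reader might infer that the DPC partial-date rule is unbounded. The opening sentence of 6.9.2.1 and the exclusion in 6.9 bound it except in the month of the last blinded dose, where a missing day leaves the bound undecidable.
- The test against randomization looks like text carried over from the DPC rule. It is still wrong as written.

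**Conclusion.** The point holds. As written, SAP 6.9.2.2 and Protocol 8.4.8.1 admit a rescued entrant's AEs on injected SRL to the open-label capsule tables, against the direction of SAP 3 and 6.9. The alternative reading leaves those AEs in no SAP TEAE table. The partial-date exclusion cannot operate once blinded treatment exceeds 30 days, with ambiguity and possible double counting essentially confined to the calendar month of the last blinded dose.

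The documents give no rescue rate, so the number affected is unknown. The interval of 0 to about 30 weeks or slightly more rests on assumed titration paths. A reader might take the upper figure as a maximum, but escalation at any time through Week 24 and unscheduled visits mean that no maximum is established. With about 50 randomized, one patient is at least about 1/50 = 2 percentage points of the OLE set, though a patient counts once per term, so an added AE matters only if the term is otherwise absent for that patient.

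Nor do the documents support inferring harm to the randomized comparison. Safety is descriptive, no efficacy analysis changes, completers entering the OLE are essentially untouched apart from partial dates, and the on-treatment DPC table changes only for AEs with a missing onset day. It should be fixed because the rule is wrong as written and the repair is cheap.

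**What to change.** 1. In SAP 6.9.2.2 and Protocol 8.4.8.1, open the OLE TEAE window at the first open-label dose for onset, worsening and partial dates. State which single period takes an AE dated on the day of that dose. This is needed because Protocol Appendix A makes Week 36 also the first OLE visit, so the last blinded and first open-label doses may share a date.
2. In the OLE partial-date rule, replace the test against randomization with one against the first open-label dose, and let the first branch apply only to months after the anchor month.
3. In the DPC partial-date rule, write in the upper bound at the last blinded dose.
4. Keep the on-treatment DPC table. Report AEs after the last blinded dose and before the first open-label dose (or to Week 36 for patients who do not enter the OLE) in one listing or descriptive table by randomized arm.
5. Reconcile Protocol 7.1 with 8.4.8.1 on where the DPC TEAE window ends.

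The cost is SAP and protocol wording plus one descriptive output from dates already collected.

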## 5.5 FOLLOW-UP PERIOD

Patients who discontinue study medication any time during the OLE period, for any reason, or have completed the 36-week DPC period on study medication and are ineligible or opt not to continue into the OLE period, will revert to their prior injectable SRL treatment (prior to Screening period) or other treatment as determined by their physician and will be followed-up for 12 weeks consisting of an in-clinic follow-up visit 4 weeks ( $\pm 5$  days) after EOT and a phone call 8 weeks later ( $\pm 5$  days).

The following procedures will be performed at the in-clinic Follow-up visit:

- Vital signs and weight
- 12-lead ECG
- Laboratory tests: hematology and biochemistry
- Acromegaly directed and treatment directed physical examination
- AEs and concomitant medications recording
- Study medication accountability
- IGF-1 and GH
- Abdominal (gall bladder) ultrasound

---

 GH: five samples will be collected every  $30 \pm 5$  minutes over two hours. 2-4 hours after study medication administration in the clinic, (patients to fast 4 hours prior to and the 2 hours during GH sampling).

 GH: five samples will be collected every  $30 \pm 5$  minutes over two hours. If octreotide capsules were taken at the clinic - 2-4 hours after octreotide capsules administration, otherwise 0-2.

The following procedures will be performed during the phone call 12 weeks after EOT:

- AE
- Concomitant medications

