AEs will be assessed at all study visits throughout the study from informed consent signing. AEs reported prior to dosing on Baseline Day will be captured and considered non-treatment emergent AEs. Treatment Emergent AEs (TEAEs) will be considered all AEs that occurred from Baseline (following study medication administration) to end of core study (i.e. end of DPC period). AEs reported after termination/completion of the core study, during the Follow-up period will be reported separately. AEs reported during the OLE period will be reported separately and together with the core study. The final safety analysis will be detailed in the Statistical Analysis Plan (SAP). The date and time of each AE occurrence will be recorded.

All AEs, whether observed by the Investigator or designee or volunteered by the patient, should be recorded individually on an AE eCRF page with the following information: the specific event or condition, whether the event was present pre-study (and if so, should be captured in the medical history eCRF page), the dates and times (using the 24 hour clock, where midnight is 00:00 and noon is 12:00) of occurrence, duration, severity, relationship to study medication, specific countermeasures, outcome, and whether considered non-serious or serious, drug-related or not. AEs will be recorded from the time a patient has signed the informed consent form (ICF) and throughout the study, including the Core study, Follow-up and OLE period. Severity of the AE will be assessed by the Investigator in accordance with the definitions below. An SAE must fulfill the requirements listed in the [Section 7.2](#).

Three definitions only should be used by the investigating physician to describe the severity of the AE ([Table 1](#)). Only one severity (the worst severity) definition should be used for each AE (e.g., "mild/moderate" is not acceptable).

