### **6.9.3 Laboratory Parameters**

Descriptive summary statistics for chemistry and hematology data at each post randomization time point (both absolute and change) will be presented by final dose group and treatment group (i.e., octreotide 40, 60, 80, overall and placebo). Summaries will be provided for the DPC period and for the OLE period. In calculating the change from baseline for both the DPC and for the OLE, the baseline for the DPC period will be used.

Shift tables, summarizing individual subject changes from baseline to end of treatment will be presented for each laboratory parameter, by treatment group, using the normal ranges from the central laboratory. An additional shift analysis will be presented for glucose using the levels within the common terminology criteria for adverse events (CTCAE) version 4.03. Summaries will be provided for both the DPC period and OLE period. For both the DPC period and the OLE period summaries, baseline will be the baseline defined for the start of the DPC period.

Subjects with clinically significant abnormalities (based on investigator’s assessment) will be identified in listings.

All tabular summaries will exclude any data that was collected after a subject had discontinued study drug. Data collected after a subject had discontinued study drug will be included in listings.

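### The treatment-emergent date test for the open-label extension (OLE) has no closing date, so as written it does not exclude adverse events from the 12-week follow-up of patients who stop the capsules early

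*SAP*

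**What the plan says.** **OLE rule.** SAP 6.9.2.2 has two criteria. The first is that "AE onset date is after the end of treatment in the DPC period". The second is that "AE is ongoing, and the severity worsens during the OLE", but the date test in brackets after it again asks only for a date later than the end of DPC treatment. None of the four partial-date rules sets an upper limit. Protocol 8.4.8.1 has the same two criteria. On presentation, SAP 6.9.2.2 says: "All summaries will be presented by final dose group (i.e., 40, 60 or 80) and overall for the OLE set".

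**DPC rule.** SAP 6.9.2.1 closes its window. Onset must fall "on or before the end of treatment (last dose of blinded study drug) in the DPC period".

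**Other safety data.** SAP 6.9.3 says: "All tabular summaries will exclude any data that was collected after a subject had discontinued study drug". The same sentence stands in 6.9.4 (vital signs), 6.9.5 (ECG) and 6.9.6 (ultrasound), but not in 6.9.2 (AEs). The introduction to SAP 6.9 excludes off-drug data from DPC safety analyses. Its next sentence, on the OLE, has no such exclusion.

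**After the last capsule.** Under Protocol 5.5, patients who stop during the OLE "will revert to their prior injectable SRL treatment (prior to Screening period) or other treatment as determined by their physician". They are followed for 12 weeks, with AEs recorded at a clinic visit 4 weeks after end of treatment and at a phone call at 12 weeks. SAP 3 places data collected after the DPC period in the OLE database.

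**Separate reporting.** Protocol 7.1 says that AEs reported after the core study ends, "during the Follow-up period will be reported separately". SAP 1 gives the SAP precedence where the two documents differ.

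**The concern.** The plan limits its other safety tabulations to time on study drug and leaves that limit out for OLE AEs. A laboratory value taken four weeks after the last open-label capsule is dropped, while an AE with onset on the same day passes the treatment-emergent test.

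Long-term safety of the capsules is an objective of the OLE, and during follow-up the patient is on a different treatment. Two kinds of event show what could be misattributed:

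- **Injection-site reactions.** Protocol 1.3.2.2 presents their absence as a potential benefit of the oral route. The follow-up visit in Protocol 5.5 includes the directed examination. The Appendix B form for that examination covers such reactions and sends new findings to the AE form. A reaction to the resumed injection could therefore appear in a capsule table.
- **Acromegaly symptoms.** New or worsening symptoms are recorded as AEs of special interest (Protocol 7.1.1). Loss of control after stopping could be shown under a capsule dose that the patient no longer takes.

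**Working it through.** The plan gives no figure to reproduce. The check has three parts.

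**1. The rule applied to constructed cases.** Days run from DPC day 0. The DPC ends on day 252 (36 weeks), and the first open-label dose is taken as day 252. The SAP test is onset > 252. The closed test is first open-label dose ≤ onset ≤ last open-label dose.

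| Case | Last open-label dose | Onset | SAP test | Closed test |
|---|---|---|---|---|
| AE at OLE week 20, on drug | 588 | 392 | counted | counted |
| Stops at OLE week 8, AE 10 weeks later | 308 | 378 | counted | not counted |
| Stops at OLE week 48, AE 8 weeks later | 588 | 644 | counted | not counted |

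The two tests agree on drug and differ only after the last capsule.

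**2. Off-drug share of the counted time for one affected patient.** The follow-up is 12 weeks (SAP 3; Protocol 4.6.2 and 5.5). The weeks on open-label drug, t, are assumed. Share = 12/(t+12).

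- t = 4: 12/16 = 75%
- t = 8: 12/20 = 60%
- t = 12: 12/24 = 50%
- t = 24: 12/36 = 33%
- t = 48: 12/60 = 20%
- t = 96: 12/108 = 11%

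With the window closed at the last open-label dose, the share is 0%.

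**3. What this could do to a patient-level incidence.** Assume a constant AE rate r per patient-year, the same on and off drug. The documents give no rate. The chance of at least one counted event in T weeks is 1 − exp(−r·T/52), with T = t for the closed window and T = t + 12 for the open one.

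| Stop at week | r per year | Closed window | Open window |
|---|---|---|---|
| 8 | 0.5 | 7.4% | 17.5% |
| 8 | 1 | 14.3% | 31.9% |
| 8 | 2 | 26.5% | 53.7% |
| 48 | 0.5 | 37.0% | 43.8% |
| 48 | 1 | 60.3% | 68.5% |
| 48 | 2 | 84.2% | 90.1% |

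These are illustrations for single patients. Follow-up has only one visit and one call, so AEs may be picked up less fully there than the constant rate assumes.

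**The case against.** **The text can be read as leaving follow-up out.** The OLE rule is framed as being for OLE reporting, its worsening criterion mentions the OLE, and SAP 6.9 describes OLE safety analyses as covering data from the OLE. The protocol treats the OLE and the follow-up as separate periods. A programmer could reasonably drop follow-up events. This stands: a reader might infer that these events will certainly be tabulated under a capsule dose, and the documents do not establish that. What they establish is that the date test does not exclude them. Two programmers could produce different tables.

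**Protocol 7.1 is not a clear contradiction.** A reader might infer that the SAP overrides an instruction to report OLE follow-up AEs separately. The sentence is worded for follow-up after the core study. The one after it, on OLE events, says nothing about their follow-up, and the section leaves the final safety analysis to the SAP. This stands too. The sentence shows the sponsor's practice for one follow-up period and needs extending to the other.

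**Tabulation by relationship helps.** OLE events are also shown by investigator-assessed causality, so an injection-site reaction can appear as not related. This is partial mitigation, because the overall and dose-group tables would still contain it.

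**A cut exactly at the last dose could hide delayed drug effects.** The protocol itself looks for events after treatment: 7.4 asks for related serious events that emerge later, and 5.5 repeats the ultrasound. This is a fair point about the remedy. It is met by a stated lag and a table of later events.

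**Conclusion.** The gap is real. As written, the OLE treatment-emergent test has no closing date and does not exclude AEs from up to 12 weeks after the last capsule. Such events would be summarized under a capsule dose, unlike in the plan's other safety tables.

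The size is limited in three ways.

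- **Who is affected.** A reader might infer that every OLE patient contributes 12 off-drug weeks. Protocol 3 and footnote 4 of Appendix A confine this follow-up to patients who stop open-label treatment early and to DPC completers who do not enter the OLE. The second group is outside the OLE set (SAP 4.4).
- **How much.** For an affected patient the off-drug share of counted time runs from 75% (4 weeks on drug) to 20% (48 weeks). These are shares of time, not of events. The share for the whole table cannot be given without an OLE discontinuation rate, which the documents do not state.
- **What is affected.** Only descriptive OLE safety tables change. No hypothesis test, and no primary or secondary result, depends on this rule.

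The conclusion rests on applying the date test literally. If the sponsor intends follow-up to be excluded, the plan should say so.

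**What to change.** In both criteria of SAP 6.9.2.2 and of Protocol 8.4.8.1, add: *and on or before the last dose of open-label study drug*. This matches the DPC rule. Alternatively, use that date plus a short lag that the sponsor states in advance. Apply the same limit in the partial-date rules.

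Tabulate later AEs in a separate follow-up table, so that no delayed event is lost. Extend the Protocol 7.1 sentence on separate reporting expressly to follow-up after the OLE.

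The cost is one clause, one extra table and a small protocol wording change. No new data are needed: AE onset dates are collected, and SAP 6.9.1.2 already uses the last open-label dose date for exposure. The downside is that some delayed drug-related events move out of the main OLE table. The lag limits this, and the follow-up table keeps those events visible.
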